8.2.2.1 Subject History

At the pre-operative visit, the Subject's relevant medical and surgical history, relating to any previous neurological, cardiovascular or general substantive issues and prior ipsilateral knee surgical history should be collected and recorded in the respective eCRF. Any changes relating to the issues listed in the medical or surgical history that occur during the clinical study (i.e. during study surgical event and later) should be recorded as an Adverse Event or Serious Adverse Event, as appropriate.

8.2.3 Operative Management

The preparation of the subject for a total knee arthroplasty should follow the Surgeon's standard of care. Once the patient is ready for the first incision the surgical workflow should follow the ATTUNE® Knee System Surgical Technique Featuring the ATTUNE® Fixed Bearing Porous Knee for the devices to be implanted (hereinafter known as "Surgical Technique"). The Surgical Technique will be provided to all study Sites prior to the start of the study. Deviation from the relevant Surgical Technique must be reported as a Protocol Deviation.

Table 8.2: Protocol Requirements During Surgery

Surgical Process Detail	Protocol Instructions
Instrumentation	Surgeons are permitted to use any instrumentation specified in the current Surgical Technique for the region in which the surgery is completed.
Femur and Tibia Treatment	ATTUNE Cementless Cruciate Retaining (CR) or Posterior Stabilized (PS) Femoral Implants are to be used in combination with the ATTUNE Cementless Fixed Bearing (FB) Tibial Base implant and appropriate ATTUNE Tibial Insert.

NOTE: If a subject is enrolled in the clinical study prior to implementation of this protocol amendment and receives the ATTUNE Medial Stabilized Tibial Insert as part of the investigator's standard of care, that subject will remain in the study, but must be reconsented with the updated IRB approved ICF which includes the Medial Stabilized insert. A Protocol Deviation must be completed for use of a non-study device with the ATTUNE Cementless Tibia. Once this protocol is IRB approved, no further Protocol Deviations are required for use of the Medial Stabilized Insert from the date of IRB approval forward as long as the subject signs the consent including the Medial Stabilized Tibial Insert as an option.

In this study, bone cement must not be used with the ATTUNE Cementless Femoral or Tibial Base components. If bone cement is used on either of these components, a Protocol Deviation CRF must be recorded and the patient will continue in the study as part of the Safety Population. However, if the site is located in the US and uses DePuy Synthes Antibiotic Impregnated Bone Cement (off-label use), a Protocol Deviation CRF must be recorded and the patient will be discontinued from the study (Study Completion/Discontinuation eCRF). The subject will be replaced with another enrolled subject.

Patellar Treatment

Study subjects may be implanted with the ATTUNE Cemented Patella, ATTUNE Cementless Patella (after product availability), or not undergo patella resurfacing as part of their study procedure.

If	Then
the site is located in the US and the patella is resurfaced using an ATTUNE Cemented Patella	The site is not permitted to use DePuy Synthes Antibiotic Impregnated Bone Cement (off-label use). If this occurs, a Protocol Deviation CRF must be completed and the patient will be discontinued from the study (Study Completion/Discontinuation eCRF). The subject will be replaced with another enrolled subject.
the patella is resurfaced using an ATTUNE Cementless Patella	In this study, bone cement must not be used with the ATTUNE Cementless Patella. If bone cement is used, a Protocol Deviation CRF must be recorded and the patient will continue in the study as part of the Safety Population.

8.2.4 Post-operative Management

Immediate post-operative management including physical therapy protocol is at the discretion of the Surgeon and support staff and should follow each Surgeon's standard of care. Rehabilitation programs are often individualized.

The methods of data collection and follow-up windows have been selected to achieve the primary objective of evaluating functional responder rates from baseline to one year as measured from the KOOS questionnaire, as well as providing further data to include survivorship and performance measures out to five years. Every effort should be made to schedule the post-operative follow-up within these windows to enhance follow-up compliance. While required interval windows have been designed to be continuous to improve follow-up compliance and accommodate various standards of care across sites, this study includes preferred windows as well to increase the consistency with respect to the timing of data collection, since function is changing with time, particularly in the early recovery phase.

All follow-up visits will be conducted according to the Time and Events Table (Table 1-1), and applicable eCRFs must be submitted to DePuy Synthes Products Inc. Data collected during the post-operative management of the Subject is listed in Table 8-1.

8.2.4.1 Postoperative Data Collection Methods:

A postoperative follow-up is to be done ONLY by a clinic visit at the 6 week, 6 month, 1 year, 2 year and 5 year follow-up windows. The phone contact visit is to be done only at postoperative years 3 and 4:

The definition of a **Clinic visit** as defined by this protocol is either of the below:

- The Preferred In Clinic Method: Subject is seen in clinic, receives an assessment of the study knee including study required radiographs, the Subject completes the source document PROMs and the required data is submitted to the Sponsor as per protocol (See Time and Events Table 1-1).
- An Alternative PROMS by Mail Method + Phone Contact* (postoperative follow-up only): This method is to be done in the event the Subject is either unable or unwilling to be seen in the clinic office and agrees to complete and return the study required PROMs by mail AND attend a follow-up phone contact visit*. Upon completion of both methods of data collection (in the same interval window), an alternative clinic visit will be considered completed. This type of visit allows for the surgeon portion of the AKS and radiographs to be optional. The details associated with administration of PROMs are described in Section 8.2.1 and apply for this method of data collection A sample cover letter, Contact Form, and Phone Script are provided in Exhibit F.

The definition of a *Phone Contact visit is defined as:

A telephone call with the Study Subject (See Time and Events Table 1-1). In order to optimize the accuracy of survivorship data, enable timely capture of AEs and maximize the chance of good long- term follow-up, contact will be made with each Subject at 3 and 4 years post-operatively. These telephone contact visits will occur in between the 2yr and 5yr clinic visits and will ideally occur within the preferred window. No PROMs are to be completed.

Phone Contact visits will take the form of a telephone call where a member of the study team, typically a Research Coordinator, speaks with the study Subject. The topics to be covered and information to be collected during the call will include: confirmation of the Subject's contact information; assessment of whether there has been a revision or any adverse events to the Subject's implanted knee for the study; reminder to the Subject of their next scheduled visit and the importance of their continued study participation. As an alternative approach if in keeping with sites' standard of care, the data collected via a phone contact visit can be collected face to face (in clinic or virtual) or via mail in lieu of being done over the phone.

Note: If a full clinic visit data set is collected at the phone contact intervals (3 & 4 yrs postoperatively), the site will only be compensated for a phone contact type visit.

8.2.5 Radiographic Procedures

Radiographs are to be obtained pre-operatively and at either the 6 week or 6 month visit (1st follow-up/baseline evaluation, timeline as per the Site's standard of care) and again 1, 2 and 5 years post-operatively (within the respective windows specified in this protocol). Pre-operative radiographs are to be collected as per the Site's standard of care. AP/PA and Lateral views are required for all Subjects at the above post-operative timepoints. Skyline views should also be collected post-operatively for Subjects with an implanted patellar component. Investigators will complete questions within the eCRF regarding interpretation of the radiographs for each required set of radiographs.

Radiographic guidelines regarding image collection will be provided to Sites. Sites are also required to send all radiographs collected during the course of the study to an external image analysis facility; training on the process to transfer images will be provided prior to study start.

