Screening/Enrolment Log	S*								
Informed Consent	S								
eCRF: Subject	Е								
eCRF: Inclusion/Exclusion	Е								
eCRF: Demographics	Е								
eCRF: Medical and Surgical									
History	Е								
eCRF: Study Visit	Е	Е	Е	Е	E	Е	Е	E	Е
eCRF: 2011 AKS (Pre-op Patient Eval'n)	Р								
eCRF: 2011 AKS (Post-op Patient Eval'n)			Р	Р	Р	Р			Р
eCRF: 2011 AKS (Surgeon Eval'n)	E		E♦	E∳	E∳	E♦			E∳
eCRF: KOOS	Р		Р	Р	Р	Р			Р
eCRF: FJS-12			Р	Р	Р	Р			Р
eCRF: EQ-5D-5L	Р		Р	Р	Р	Р			Р
eCRF: Study Procedure		Е							
eCRF: Device Log		E							
eCRF: Image / Scan	Х		Х		Х	Х			Х
eCRF: Radiographic Eval'n			Х		Х	Х			Х
eCRF: Adverse Event		E*	E*	E*	E*	E*	E*	E*	E*
eCRF: Adverse Event		E*	E*	E*	E*	E*	E*	E*	E*
eCRF: Device Deficiency Summary		E*	E*	E*	E*	E*	E*	E*	E*
eCRF: Device Deficiency		F*	F*	E*	F*	F*	E*	F*	E*
eCRF: Protocol Deviation Summary	E*	E*	E*	E*	E*	E*	E*	E*	E*
eCRF: Protocol Deviation	E*	E*	E*	E*	E*	E*	E*	E*	E*
eCRF: Subject Completion/ Discontinuation	E*	E*	E*	E*	E*	E*	E*	E*	E

LEGEND:

- S = Remains on site as source document
- S* = Original remains on site as source document with copies regularly submitted to sponsor
- E = Source data transcribed onto electronic Case Report Form (eCRF) and submitted to sponsor
- E♦ = Source data transcribed onto electronic Case Report Form (eCRF) and submitted to sponsor if In Clinic Visit completed.
- E* = Source data transcribed onto eCRF and submitted to sponsor if In Clinic Visit, Alternative Visit, or Phone/Mail Contact Visit completed.
- P = Patient Recorded Outcome Measures (PROMs), completed by Subject, data entered on eCRF & submitted to sponsor
- X = X-ray image to be taken & submitted to core imaging lab for storage/analysis. Optional at Postoperative visits performed outside of clinic

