Inclusion/Exclusion	Verification of Subject as per Inclusion / Exclusion Criteria	Pre-Op Only
Demographics	Record of relevant Subject demographic information	Pre-Op Only
Medical and Surgical History	Authorized medical personnel will collect Subject's relevant medical and surgical history relating to any previous cardiovascular, neurologic, general medical history and previous surgeries on the affected knee.	Pre-Op Only
Study Visit	Assists study site to verify that study visit occurred in the appropriate interval and by the appropriate means (at clinic, by mail or by phone). Prior approval from Sponsor required for Site to exercise mail or phone options.	Pre-op & Post-op
Pre-operative AKS 2011 ³⁹ Patient reported section	Pre-op O	
Post-operative AKS 2011 – Patient reported section	below. The total time for completion per study Subject is approximately 20-25 minutes.	Post-op Only

Case Report Form	Details of Evaluation	Pre-Op/ Intra- op/Post—Op
Knee injury and Osteoarthritis Outcomes Score (KOOS)		Pre-op & Post-op
Forgotten Joint Score (FJS-12)		Post-op
EQ-5D-5L		Pre-op & Post-op
AKS 2011 – Surgeon reported section	The Investigator or appropriately trained designee must complete the OBJECTIVE KNEE INDICATORS section that assesses the Subject's alignment, instability, and joint motion.	Pre-op & Post-op
Image/Scan	Date and details of Radiographs collected at each required timepoint. AP/PA, Lateral and Skyline (as applicable) radiographs will be obtained post-operatively (Section 8.2.7) Pre-operative radiographs (taken as per the Sites standard of care) can be taken up to -180 days prior to the surgical event (or older at the discretion of the PI). Pre-operative Radiographs provide background information only, and do not constitute either a primary or secondary endpoint. Post-operative radiographs must be taken as per study-required Image Acquisition Protocol (IAP).	Pre-Op & Post-Op
Radiographic Evaluation	Surgeon evaluation of post-op radiographs	Post-Op
Study Procedure	Description of Subject's surgical procedure including such items as configuration used, surgery time, tourniquet time, surgical technique details etc.	Intra-Op
Device Log	Identification of devices implanted, including product codes, lot numbers and Universal ID code/device identifier (if available).	Intra-Op
Adverse Event Summary	Summary of all recorded AEs for each subject	As required (Intra- Op and/or Post- Op)

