8.2.2 Pre-operative Management

Prior to surgery, the data in Table 1-1 (the Time & Events Table) must be collected for each enrolled Subject. The interval for obtaining the Informed Consent and pre-op assessments is from -90 days through day -1 (1 day prior to surgery) as designated on the Time & Events Table (Table 1-1). The -90 day time frame is important to support PROMs being collected closer to the time of surgery since it is anticipated that there may be deterioration in function as the patient awaits surgery.

The interval for obtaining preoperative radiographs is extended to -180 days (or older at discretion of PI*) to day -1 (day prior to surgery) so that study Subjects would not need to have repeat radiographs if any radiographs that had been taken as standard of care prior to the Subject being enrolled were the required views. This will be allowed to minimize the study Subject's unnecessary exposure to radiation.

*Note: it would be preferred if the radiographs were taken from -90 days through -1 day, however, if radiographs are available that exceed the 180 day maximum timepoint, they can still be used if they are thought to be acceptable for preoperative surgical planning (per the surgeon's standard of care) at the discretion of the Principal Investigator (PI). If the preoperative x-rays are not able to be uploaded to the MMI system, submitted to MMI via CD, available via hard copy for courier to MMI, or are not deidentifiable, they should be repeated.

Once written informed consent is given, the below will be followed:

- Pre-operative Patient Reported Outcome questionnaires, Inclusion/Exclusion, Demographics, Medical and Surgical History, 2011 American Knee Society Score surgeon (AKS) and Image/Scan CRFs are to be completed.
- The TKA surgical details and all intra-operative complications, regardless of their relationship to the procedure or device, are captured on eCRFs for subsequent analysis.
- In clinic follow-up intervals include 6 weeks, 6 months, 1 year, 2 years and 5 years postoperative. Post-operative radiographs will be taken at either the 6-week OR the 6-month follow-up (if x-rays are taken as standard of care at both visits then the 6-week x-rays should be used) and again at 1 year, 2 years and 5 years.
- Subjects will be contacted by phone or by mail at 3 and 4 years post-op to optimize
 accuracy of the survivorship data, enable timely capture of AEs and maximize the chance
 of good long term follow-up.

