8.6 Revisions

A "revision" is defined as a surgical procedure of the affected knee where one or more of the TKA components (metal femoral component and/or metal tibial base, polyethylene insert, or patella polyethylene resurfacing component) are removed. Should it be necessary for the Subject to undergo a revision of any ATTUNE Cementless Femoral and/or Tibial Base component between the time of enrolment and completion of the study data acquisition, the Subject is to be withdrawn from study participation. Thus, both an Adverse Event (AE) eCRF and the Subject Completion/Discontinuation eCRF must be completed (see Table 8-9). Note that if a tibial insert is exchanged and/or a resurfaced patella is revised, but both the femoral and tibial base components remain, then an AE eCRF must be completed, but the subject is not to be withdrawn from the study.

A "re-operation" is defined as any surgical procedure of the affected knee in which none of the TKA components are removed. Examples include irrigation & debridement without tibial insert exchange or the resurfacing of a previously unresurfaced patella. These subjects are not to be withdrawn. An Adverse Event (AE) eCRF must be completed.

Table 8-10: Revision and Reoperation Examples

Example	Actions	Follow Up
Removal / revision of metal Tibial Base and/or Femoral component	 Complete Adverse Event eCRF Complete Revision/Reoperation eCRF Complete Study Completion/Discontinuation eCRF 	Do not continue
Tibial Insert polyethylene exchange	Complete Adverse Event eCRF Complete Revision/Reoperation eCRF	Continue
Revision of a previously resurfaced patella	 Complete Adverse Event eCRF Complete Revision/Reoperation eCRF 	Continue
Resurfacing of a previously unresurfaced patella in combination with a Tibial polyethylene exchange	 Complete Adverse Event eCRF Complete Revision/Reoperation eCRF 	Continue

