9.8.4.2 Secondary Endpoints and Associated Hypotheses

The secondary endpoints in this study are:

- Type and frequency of Adverse Events and Device Deficiencies.
 - Functional responder rates with an objective performance criteria (OPC) of 85% as measured by the KOOS questionnaire for all subjects (CR FB and PS FB combined) at the 1 year timepoint.
- The change from preoperative baseline to the 6 week, 6 month, 1 year, 2 year and 5 year timepoints in functional outcomes and quality of life assessments, as measured using additional patient reported outcomes measures (PROMS):
 - o AKS 2011
 - KOOS (all subscores)
 - FJS-12 (changes post-operatively only)
 - o *EQ-5D-5L*
- Implant survivorship of the ATTUNE Cementless FB Tibial Base using Kaplan-Meier survival analysis at 1, 2 and 5 year timepoints.
- Investigator-conducted radiographic analysis of the tibial and patellar components at 6 weeks/6 months, 1, 2 and 5 years after surgery.

All secondary endpoint analyses may be conducted after all patients have passed the recommended study window (ex. with a 2-year follow-up analysis conducted after all subjects have passed 790 days post-op). All analyses at these time points will be conducted again with final data, along with endpoints which have a 5-year follow-up time point, with locked data at the close of the study.

A Kaplan-Meier survivorship model will be used to estimate survivorship rates (where a revision is defined in Section 8.6) along with a two-sided, log-log based 95% confidence intervals; this analysis will be conducted on the Safety analysis set.

The types and frequencies of adverse events that occur throughout the study will be tabulated by MedDRA system organ class (SOC) and preferred term (PT) for all Subjects in the Safety analysis set. The proportion of Subjects experiencing each complication (PT within SOC) will be presented, and a 95% confidence interval will be estimated with the binomial exact method.

All other specified secondary endpoints will be presented with statistical summaries at each respective time point; these secondary endpoint analyses will be carried out with all data on subjects in the Per Protocol analysis set.

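### The radiographic endpoint has a named baseline film but no planned within-knee comparison with it, so the visit summaries give net change in prevalence rather than the rate of new interface findings

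*Combined protocol and SAP*

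**What the plan says.** **Reference film.** Section 8.2.5 schedules the first post-operative films "at either the 6 week or 6 month visit (1st follow-up/baseline evaluation, timeline as per the Site's standard of care"). If a site takes films at both visits, section 8.2.2 settles which counts: "if x-rays are taken as standard of care at both visits then the 6-week x-rays should be used". Table 8-1 in section 8.2.1 removes the only earlier candidate: "Pre-operative Radiographs provide background information only, and do not constitute either a primary or secondary endpoint".

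**What is recorded.** Section 8.2.5: "Investigators will complete questions within the eCRF regarding interpretation of the radiographs for each required set of radiographs". The questions themselves are not reproduced in the documents.

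**What is analysed.** Section 9.8.4.2 lists the investigator's radiographic reading of the tibial and patellar components at 6 weeks/6 months and at 1, 2 and 5 years. The only method that reaches it is the general one: "All other specified secondary endpoints will be presented with statistical summaries at each respective time point", on the Per Protocol set. Section 9.8.1 makes that counts and percentages for categorical variables. The corresponding row of Table 6-1 lists only 1, 2 and 5 years.

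**Which knees have films.** Table 1-1 marks post-operative films "Optional at Postoperative visits performed outside of clinic", and section 8.2.4.1 says of the mail-plus-phone visit: "This type of visit allows for the surgeon portion of the AKS and radiographs to be optional". After revision of the femoral component or tibial base, section 8.6 states that "the Subject is to be withdrawn from study participation". Section 9.5 rules out imputation.

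**The concern.** Section 3.2 justifies the follow-up partly by the first year, when problems with initial cementless fixation would show. For that purpose the informative radiographic quantity is how many knees acquire an interface finding they did not have on the first film. Percentages at separate visits do not give this directly. They combine new findings, findings that have resolved, and changes in which knees were filmed.

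The plan does state a reference for its other repeated measures: the pre-operative value for AKS, KOOS and EQ-5D-5L, and the first post-operative visit for FJS-12 (Table 6-1). The radiographic endpoint has a designated baseline and no stated use of it. Section 3.1 says the data will support CE marking of the tibial base, so a clear account of new interface findings would be useful to the reader of the report.

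**Working it through.** The plan gives no figure for this endpoint, so there is nothing to reproduce. The check is what the visit percentages identify, followed by an example. The documents give no prevalence, resolution rate or film-loss rate; **all counts below are assumed**, apart from 300, which is the planned minimum per configuration.

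**1. What the difference between visits contains.** Suppose every knee with a later film also has a first film. Then

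later % − first % = (new − resolved)/paired + (first-film % among paired knees − first-film % among all knees).

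The first term is net change; the second is selection. The difference equals new/paired only if nothing resolves and the selection term is zero.

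**2. Loss unrelated to the finding, none resolving.** First film 30/300 = 10.0%.
- 15% of films missing: 30 × 0.85 = 25.5 positive knees remain among 255. With 4 new: 29.5/255 = 11.6%, a rise of 1.6 points. Paired rate 4/255 = 1.6%.
- 5% missing: 30 × 0.95 = 28.5 among 285. With 2 new: 30.5/285 = 10.7%, a rise of 0.7 points. Paired rate 2/285 = 0.7%.

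Here the planned summaries recover the new-finding rate.

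**3. Loss related to the finding, none resolving.**
- 15% missing, 8 of the 45 lost knees positive. Loss is 8/30 = 26.7% against 37/270 = 13.7%, a ratio of 1.9. Then 22 + 4 = 26, and 26/255 = 10.2%. By the identity: 4/255 = 1.57 points, plus 22/255 − 30/300 = 8.63 − 10.00 = −1.37 points, gives 0.20 points.
- 5% missing, 3 of the 15 lost knees positive: 27 + 2 = 29, and 29/285 = 10.2%.

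The visit percentages stay near 10% in both cases.

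**4. Nothing missing, some findings resolve.** With 10% at both visits, new = 300 × [0.10 − (1 − r) × 0.10] = 30r, where r is the fraction of first-film findings that resolve. So r = 0, 0.10 and 0.20 give 0, 3 and 6 new findings. The limit of 30 needs every finding to resolve.

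**5. What a paired table would report in step 3** (Clopper-Pearson 95% limits: the 0.025 quantile of Beta(x, n − x + 1) and the 0.975 quantile of Beta(x + 1, n − x)).

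| Case | New / all paired | New / paired and negative on first film |
|---|---|---|
| 15% missing | 4/255 = 1.6% (0.4 to 4.0%) | 4/(255 − 22) = 4/233 = 1.7% (0.5 to 4.3%) |
| 5% missing | 2/285 = 0.7% (0.1 to 2.5%) | 2/(285 − 27) = 2/258 = 0.8% (0.1 to 2.8%) |

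**6. Interval from first film to 1-year film.** Required windows (Table 9-1): shortest 304 − 303 = 1 day, longest 669 − 1 = 668 days. Preferred windows (Table 1-1: days 28-56 or 166-194, then 335-395): shortest 335 − 194 = 141 days, longest 395 − 28 = 367 days.

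**The case against.** **The form may already do this.** If the eCRF asks about new or progressive change at each film, a visit count reports it. The questions are not shown, so this stands as a condition on the point. Films also go to an external imaging facility, but its analyses are not described, so that route settles nothing either way.

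**Safety tables cover part of the ground.** Exhibit B allows osteolysis to be coded from a radiograph without a revision. All device- or procedure-related adverse events are reportable (section 8.3), and section 9.8.4.2 gives subject-level proportions with exact 95% intervals. Kaplan-Meier on the Safety set counts revisions. What is left is interface change in unrevised knees that the investigator does not report as an adverse event. That remainder is narrower than all interface change, but no planned table shows it unless the form does.

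**The flat percentages depend on assumptions.** A reader might infer that the planned summaries will hide new findings. The documents do not support that: steps 3 and 4 need selective loss or resolution, and nothing in the plan says that either will occur. Under step 2 the visit summaries suffice. The 6-week/6-month time point is also in section 9.8.4.2, so first and later percentages can be read side by side.

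**Pairing does not cure drop-out.** Correct. A table of knees with both films leaves out the same knees, and selective loss still affects it. What it does is separate new from resolved findings and make the missing pairs visible.

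**It can be produced later.** Also correct, if the form records the findings at each film. Specifying it now fixes the comparator, the denominator and the handling of unpaired knees before the data are seen.

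**Conclusion.** The point stands as a cheap improvement. The plan names a baseline film and states no within-knee comparison with it. Unless the eCRF captures progression, the visit summaries give net change in prevalence, which equals the new-finding rate only when no finding resolves and film loss is unrelated to the finding.

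The size cannot be derived from the documents. In the assumed example the gap between the two measures runs from nil (step 2) to about 1.4 points of a 1.6% paired rate (15% missing, selective loss).

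Two stronger readings should be resisted. One is that the radiographic analysis is invalid or that fixation problems would go undetected: the endpoint is descriptive with no threshold, readings are collected for each required film set, and revisions and reported events are analysed elsewhere. The other is that the comparison interval will typically be as erratic as 1 to 668 days: that is the extreme of the required windows, and the preferred windows give 141 to 367 days.

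Priority is low. The KOOS primary analysis, the sample size and study success are unaffected.

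**What to change.** First check whether the eCRF already records new or progressive change. Then add to section 9.8.4.2:

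- One descriptive within-knee shift table, for each interface finding the eCRF records, of the first post-operative film against 1, 2 and 5 years. Use the 6-week film when both exist, as section 8.2.2 already provides.
- The number and percentage with a new finding among knees that have both films and were negative on the first, and also per all paired knees, each with an exact 95% interval.
- The number of knees without a pair, by reason (off-site visit, revision, lost) and by first-film status, because the paired table does not itself remove selective loss.
- Whether the first film fell in days 1-90 or 91-303.

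Keep the visit summaries.

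**Cost.** One table and a short paragraph, with no new films or visits. No form change is needed provided the eCRF already records the interface findings at each film. The paired table rests on fewer knees than the visit summaries: 255 paired knees, or 233 of them negative on the first film, against 300 in the 15% example.
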